SECONDARY OBJECTIVES	SECONDARY OBJECTIVES: - To evaluate changes in office systolic blood pressure, the combination of SBP measured in HBPM and day ABPM and 24-hour SBP before and 3 months, 6 months, 1 year, after DNR. - Evaluate the evolution at 3 months, 6 months, 1 year, of the drug burden in antihypertensive treatment (DDD), the percentage of patients having reached the blood pressure target and the win ratio. - Evaluate the development of renal artery stenosis before and 6 months, 1 year, after DNR. - Evaluate the evolution of creatinine levels before and 6 months, 1 year, after DNR. - Evaluate the occurrence of other complications related to hypertension or to the procedure itself. - Comparison of responders and non-responders to the procedure (24h ABPM systolic blood pressure decrease of 5 mmHg or more and/or the diminution of the medical burden by at least one therapeutic class without SBP increase compared to baseline). - Evaluate the performance of known predictors of response to renal denervation in our population. - Describe the type of center performing the procedure, the context in which DNR is performed, patient characteristics and care pathways.
METHODOLOGY	Research that does not involve the human person, as it involves the prospective, retrospective, descriptive and comparative use of multicentric data from routine care.
TYPE OF DATA COLLECTED	The data collected are detailed below: 
 • Administrative data : - centre number followed by a hyphen (-) then the patient's number - collection of the patient's non-objection to participate in the FRiEND register - date of inclusion, date of procedure

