	
Codage :
 
The data will be pseudonymised by coding: patients will be identified as follows: centre number followed by a hyphen (-) then the patient number coded number specific to the research indicating the order of inclusion of subjects (ex. 01-001). The list of correspondences between the patient code and his identity will be kept in each participating center, in the service server, by the investigator on an Excel file.

DATA STORAGE PERIOD	
Personal data relating to persons taking part in research, and processed for this purpose, may be kept in the information systems of the controller, the participating centre or the healthcare professional involved in the research for a maximum of 2 years after the last publication of the results of the research or, if there is no publication, until the final report of the research is signed.
 
The personal data of the professionals involved in the research may not be kept for more than fifteen years after the end of the last research project in which they participated.
 
It is then archived on paper or electronically for a period of time in accordance with the regulations in force. The data must then be deleted.

DESCRIPTION OF STATISTICAL ANALYSIS OF DATA	
NUMBER OF SUBJECTS TO BE INCLUDED
 
The number of subjects included will correspond to the number of patients undergoing renal denervation for hypertension at the Grenoble University Hospital and in the various French centres participating in the study during the study period (the estimation is currently 100 per year).
 
DATA ANALYSIS
 
The database will be stored in accordance with the signed investigator commitment, on a secure database certified to keep health data, and linked to the REDCAP system supporting the eCRF. The analyses will be carried out at the University Cardiology Clinic of the Grenoble University Hospital by [name] and [name] with the help of the SFHTA, using SPSS version 21 (SPSS Corp, Somers, NY) and STATA® 14.1 (Stata Corporation, College Station, TX).

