	
Statistical analysis: Absolute values, percentages and means (SD) will be calculated to describe the population.
 
The differences between the variables before and after the RDN will be tested using either a paired t-test for normally distributed data or a Wilcoxon test, and a paired Chi2 or a Fisher test. For univariate analysis of variables between the RDN responder groups (5 mmHg reduction in 24h SBP) and non-responders, we will use the t-student analysis of variance test or non-parametric tests for continuous variables, and chi2 or Fisher tests for categorical variables. A multivariate analysis will also be performed.

PEOPLE INCLUDED IN THE RESEARCH	
Number of subjects: Estimation of 100 per year (might be less in the first year, then more as RDN implementation in France increase)
 
Inclusion criteria: Adult (> 18 years old) hypertensive patients treated with RDN in France whatever the catheter and the indication. This might include retrospective data for patient already treated with RDN in the past.

	
Non-inclusion criteria: RDN not proposed to the patient, patient opposing the collection and use of his/her data for research purposes.
 
Information and traceability procedures for non-objection/opposition :
 
Patients will be fully and fairly informed, in comprehensible terms, of the objectives of the study and the nature of the information collected, and of their right to object at any time to the use of the data collected. They will be given an information letter and the non opposition will be written down in the medical records of the patient. If the subject objects to their personal health data being processed for research purposes, this objection will be recorded in their medical file. This right of objection may be exercised at any time by any means with either the person responsible for the research or the establishment holding the data, which undertake to respond to the request within a maximum of 2 months.
 
Retrospective patients will be informed by post. On receipt of this letter, the patient will have 4 weeks to object.

ETHICS	NA

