WHY THE STUDY IS IN THE PUBLIC INTEREST	The legal basis for this data processing is Article 6 of the General Data Protection Regulation (GDPR), namely the performance of a mission of public interest assigned to the data controller and the legitimate interests pursued by it. In addition, under Article 9 of the GDPR the data controller may exceptionally process special categories of data, including health data notably for scientific research purposes.
EXPECTED BENEFITS	
To objectively evaluate RDN performance, patients and center profiles and care pathway in the various French centres participating to the registry, and to investigate whether there are any predictive factors (on the basis of the initial clinical and biological work-up) for the outcome in terms of lowering blood pressure, in order to better target patients who could benefit from this type of procedure in the future.
 
Provide informed, independent data to the health authorities to support reimbursement decisions and the choice of indications.

Study schedule

Visits	During hospitalization for RDN	1 month after RDN	6 months after RDN	12 months after RDN
Patient information	X			
RDN indication verification	X			
Blood sample	X			
Imaging examinations	X			
Medical history collection	X			
Clinical examination	X	X	X	X
Ongoing therapy collection	X	X	X	X
Adverses events recording	X	X	X	X
Blood Pressure and heart rate recording	X	X	X	X
Blood sample				
Ionogram (Na, K), glucose level, creatininemia (DFG MDRD), uricemia	X	X	X	X
Total Cholestérol, HDL, LDL triglycerides, NFP				X
Microalbuminuria, proteinuria				X
Clinical examinations				
Home Blood Pressure Measurement		X	X	X
Ambulatory Blood Pressure Measurement				X
Renal Arteries ultrasound				X
Renal arteries angioCT				X

Bibliographie :

1. Adherence to Antihypertensive Treatment and the Blood Pressure-Lowering Effects of Renal Denervation in the Renal Denervation for Hypertension (DENERHTN) Trial. Azizi M, Pereira H, Hamidouche I, Gosse P, Monge M, Bobrie G, Delsart P, Mounier-Véhier C, Courand PY, Lantelme P, Denolle T, Dourmap-Collas C, Girerd X, Michel Halimi J,

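### Seeking predictors of response by splitting the 24-h SBP change at 5 mmHg loses power and makes baseline SBP look predictive when the true effect does not depend on it

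*Protocol*

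**What the plan says.** In the Protocol, the statistical analysis part of the section describing the analysis of data sets the comparison: "For univariate analysis of variables between the RDN responder groups (5 mmHg reduction in 24h SBP) and non-responders". For it, "we will use the t-student analysis of variance test or non-parametric tests for continuous variables, and chi2 or Fisher tests for categorical variables". One further sentence follows: "A multivariate analysis will also be performed". The outcome scale, the covariates and the handling of baseline SBP in that last analysis are not given.

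Two other places depend on this comparison. The secondary objectives include "Evaluate the performance of known predictors of response to renal denervation in our population". The expected benefits section looks for "predictive factors (on the basis of the initial clinical and biological work-up) for the outcome in terms of lowering blood pressure", and gives the purpose as "in order to better target patients who could benefit from this type of procedure in the future".

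The secondary objectives also define a responder more widely than the statistical section does: "24h ABPM systolic blood pressure decrease of 5 mmHg or more and/or the diminution of the medical burden by at least one therapeutic class", provided that SBP does not rise. The statistical section names only the 5 mmHg criterion.

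**The concern.** Splitting a continuous change treats a fall of 4 mmHg and a rise of 10 mmHg alike, and a fall of 6 mmHg and one of 30 mmHg alike. That costs power in a registry of modest size.

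The second problem is bias. The observed fall is the baseline reading minus the follow-up reading. A patient whose baseline reading was high by chance is more likely to cross 5 mmHg, whatever the procedure did. The responder group therefore has a higher baseline SBP by construction, and an ordinary t-test will often report this as a finding.

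The results are meant to guide which patients are offered the procedure in future, and the expected benefits section also mentions the choice of indications. A statement that patients with higher baseline 24-h SBP respond better would be an easy conclusion to draw from this analysis, and it could be purely regression to the mean.

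**Working it through.** **Inputs from the Protocol.** Cut-off 5 mmHg. Accrual: "the estimation is currently 100 per year". Inclusions run from April 2025 to April 2027, so 100 × 2 = about 200 prospective patients, plus an unstated number of retrospective ones. The Protocol gives no SD, effect size, alpha or power, so there is no planned figure to reproduce.

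**Assumptions.** Two-sided alpha 0.05; mean fall 6 mmHg; SD of change 12 mmHg for the power calculation; between-patient SD of true 24-h SBP 10 to 14 mmHg; within-patient (error) SD 5 to 7 mmHg; SD of the true effect 0 to 10 mmHg. The true effect is independent of true baseline SBP throughout.

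**1. Power lost by the split.** Relative efficiency is φ(t)² / [p(1 − p)], with t = (5 − mean fall)/SD and p the responder share.
- t = (5 − 6)/12 = −0.083, φ(t) = 0.3976, p = 0.533.
- Efficiency = 0.1581/0.2489 = 0.635, so 200 patients act like 200 × 0.635 = 127.
- Continuous change, correlation 0.2: atanh(0.2) × √197 = 2.85; power = Φ(2.85 − 1.96) = 0.81.
- After the split: atanh(0.2) × √124 = 2.26; power = Φ(2.26 − 1.96) = 0.62.
- Simulation agrees (0.81 against 0.62). Efficiency is 0.58 to 0.64 for mean falls of 0 to 10 mmHg and SDs of change of 10 to 15.

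**2. Baseline SBP in responders and non-responders.** Let baseline = T + e₁ and follow-up = T − effect + e₂, so fall = effect + e₁ − e₂. Then Cov(baseline, fall) = σw², SD(fall) = √(2σw² + σeffect²), and the expected baseline gap is

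σw²/SD(fall) × φ(t)/[p(1 − p)].

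For σw = 7 and σeffect = 5: SD(fall) = 11.09, and 49/11.09 × 1.60 = 7.1 mmHg. For σw = 5 and σeffect = 10: SD(fall) = 12.25, and 25/12.25 × 1.60 = 3.3 mmHg.

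Simulation, n = 200, 3,000 runs per row, t-test of baseline SBP between the groups:

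| Between-patient SD | Within-patient SD | SD of true effect | Gap (mmHg) | p < 0.05 |
|---|---|---|---|---|
| 10 | 5.7 | 0 | 6.5 | 98% |
| 12 | 7 | 0 | 7.9 | 99% |
| 12 | 5 | 0 | 5.7 | 88% |
| 14 | 7 | 5 | 7.0 | 90% |
| 14 | 5 | 5 | 4.6 | 59% |
| 14 | 5 | 10 | 3.3 | 35% |

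The nominal rate is 5%. For the fourth row the rate is 64% at n = 100 and 98% at n = 300. A within-patient SD of 10 would widen the gap to about 11 mmHg with a constant effect.

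**3. Which other variables are affected.** The fall contains e₁ but not T. A covariate related to T alone has zero covariance with the fall: with correlation 0.3 or 0.5 to T, the split flags it in 4% to 6% of runs. A covariate correlated 0.5 with the observed baseline reading, and so sharing its error, is flagged in 12% to 52%.

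**4. Candidate replacements.**
- Logistic model on the same split: baseline SBP is still flagged in 90% of runs (fourth-row SDs).
- Continuous change, no baseline term: covariates related to T are flagged at 4% to 5%. Baseline SBP is still flagged (49% to 100%), so the continuous scale restores power but does not remove the coupling.
- Follow-up SBP on covariate plus baseline SBP: a covariate correlated 0.5 with T, and with no effect, is flagged in 18% to 74% of runs, because the error-prone baseline only partly adjusts for T.

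**The case against.** The strongest reply is that this is a secondary, exploratory aim of a descriptive registry, that a multivariate analysis is announced, and that its details may sit in a statistical analysis plan. Part of this stands. The aim is secondary, and the missing model details are not in themselves a fault. But the Protocol does fix the split and the tests, and a multivariate model on the same split inherits both problems.

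The wider responder definition in the objectives would probably dilute the coupling, since some patients would qualify through fewer drug classes. It is still a dichotomy, and the statistical section does not use it.

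Several stronger readings are tempting and not supported:
- A reader might infer that anything correlated with baseline SBP becomes a false predictor. It does not: a covariate linked to blood pressure only through its long-term level is tested at about the nominal rate.
- A reader might infer that a false baseline finding is almost certain. Rates of 94% or more mostly come from assuming the same true effect in every patient. With a varying effect and smaller measurement error, the rate drops to about one third.
- A reader might infer that true predictors will be missed. Power is reduced, not lost: at correlation 0.25 and n = 200 it is still about 0.81 after the split, against 0.95.
- A reader might infer that adjusting for baseline SBP is the cure. As a main analysis it creates false predictors of its own.

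**Conclusion.** The point holds in a limited form. The stated analysis wastes a little over a third of the information (efficiency about 0.64 at a mean fall of 6 mmHg). It also gives baseline 24-h SBP, and readings that share its error, a false appearance of predicting response in about one third to 99% of simulated registries of 200 patients, against a nominal 5%.

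The direction of the baseline artefact follows from the algebra for any within-patient variability above zero. Its size rests on assumed SDs, on an effect unrelated to baseline, and on n = 200, which leaves out retrospective patients; more patients would make the artefact more often significant. The primary endpoint is not touched. The point should be dealt with because the Protocol links these results to the selection of future patients.

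**What to change.** In the statistical analysis text:
- Make the main predictor analysis, including the multivariate model, a linear model of the continuous 12-month change in 24-h SBP, without baseline 24-h SBP as a covariate. With that covariate, the other coefficients are the same, apart from sign, as in the follow-up-on-baseline model.
- Keep the 5 mmHg responder split for description, and use one responder definition in both the objectives and the statistical section.
- State that an association of baseline 24-h SBP, or of other baseline readings that share its error, with response will not be interpreted as prediction, because regression to the mean produces it. This sentence is needed even with the continuous outcome.
- Show the model adjusted for baseline 24-h SBP as a sensitivity analysis only, with the caution that error in the baseline reading can make covariates related to true blood pressure look predictive.

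The cost is wording only, with no new data. The result is slightly less simple to present than two groups.

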	 Data from the investigator's department only (coordinating and associated centers)  Data from several departments of the CHU Grenoble Alpes or from a department other than that of the investigator (if the investigator is at no time involved in the care of the persons targeted by the research).
DATA COLLECTION SCHEDULE	
Prospective and retrospective research :
 
 - 3-year register (start of collection april 2025 - end of inclusions april 2027, follow-up : 1 year) 
For retrospective patients, data collection will be done from clinical database from january 2010. A 4-week delay must be observed between the sending of information letters and the start of data collection.
 
 - End of follow-up: april 2028. - Annual analysis of data from patients who have undergone RDN and follow-up at 1 month, 6 months, 1 year after the procedure.
DATA COLLECTION	
Collection :
 
The data collected will be those from routine follow-up at 1 month, 6 months, 1 year of all patients benefiting from a RDN procedure and included in the registry. After the procedure, the investigator in each participating centre will manage the follow up of the patient. As the study is purely observational, it does not require any specific follow-up visits, but includes the collection of data obtained during routine follow-up visits. The registry does, however, include data collection at fixed times after procedure. The data reported in the Redcap file will be the data available closest to the theoretical day of collection.
 
Patients who have been lost to follow-up should be investigated through the referring doctors to RDN and/or by family members or any other person whose name appears on the patient liaison form. In the absence of any information, a search for the patient's possible death will be carried out by consulting the https://deces.matchid.io/searchqui website, including the INSEE source for deaths (the search will be carried out by birth name).
 
In case of the patient's death, the medical record is first checked to ensure that the patient has "no objection" to the use of his or her health data for research purposes.
 
Clinical data collection will be based on the source documents.

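### The named tests ignore centre, so the standard error of the mean BP change may be understated and any centre-level variable in the responder comparison may be tested above its nominal level

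*Protocol*

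**What the plan says.** METHODOLOGY in the Protocol describes "prospective, retrospective, descriptive and comparative use of multicentric data from routine care". Under DATA COLLECTION, "the investigator in each participating centre will manage the follow up of the patient"; there are no study-specific visits, and the value recorded is the one nearest the theoretical date.

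Under DESCRIPTION OF STATISTICAL ANALYSIS OF DATA, before/after differences, which include the primary endpoint (home SBP at 1 year), "will be tested using either a paired t-test for normally distributed data or a Wilcoxon test", with a paired chi-square or Fisher test for categorical data. The plan for comparing the two response groups is this: "we will use the t-student analysis of variance test or non-parametric tests for continuous variables, and chi2 or Fisher tests for categorical variables". One further sentence announces a multivariate analysis, with no model, covariates or handling of centre. No passage mentions a centre effect, a random effect or clustered standard errors.

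Type of centre and operator speciality are collected. SECONDARY OBJECTIVES asks only that type of centre be described. EXPECTED BENEFITS lists an objective evaluation of "RDN performance, patients and center profiles and care pathway in the various French centres" and says the results are meant to inform reimbursement decisions.

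**The concern.** Every test the Protocol names takes each patient as an independent observation. Patients treated in one centre share an operator or team, a choice of catheter and indication, habits of drug adjustment and the timing of routine visits. Their blood pressure changes may therefore resemble each other more than those of patients from different centres.

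Two results would suffer. The first is the precision attached to the mean change in home SBP, the main figure intended for the health authorities. The second is any comparison of responders with non-responders on a variable that is constant, or nearly so, within a centre. Such a comparison mixes the effect of the variable with ordinary variation between centres and can make centre profile look like a driver of response when it is not. The responder comparison is not limited to particular variables, so a centre-level variable can enter it.

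**Working it through.** **Inputs from the Protocol.** Recruitment: "the estimation is currently 100 per year". Schedule: "start of collection april 2025 - end of inclusions april 2027, follow-up : 1 year". Two inclusion years × 100 = about 200 prospective patients, plus an unstated number of retrospective patients from 2010 onward. The 100 per year is a forecast, so there is no sample-size calculation to reproduce.

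**Assumptions, not in the Protocol.** Nominal two-sided level 5%; K = 10, 20 or 40 centres; intraclass correlation (ICC) of the change within centre 0.01 to 0.10; equal centre sizes m = 200/K unless stated.

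**Formulas.**
- Design effect: DE = 1 + (m − 1) × ICC.
- True SE / naive SE = √DE.
- True error of a nominal 5% test of the mean change or of a centre-level factor = 2 × [1 − Φ(1.96/√DE)].

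Example, 20 centres and ICC 0.05: DE = 1 + 9 × 0.05 = 1.45; √1.45 = 1.204; 1.96/1.204 = 1.63; error = 10.4%.

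| Centres (m) | ICC 0.01 | ICC 0.02 | ICC 0.05 | ICC 0.10 |
|---|---|---|---|---|
| 40 (5) | DE 1.04, 5.5% | 1.08, 5.9% | 1.20, 7.4% | 1.40, 9.8% |
| 20 (10) | 1.09, 6.0% | 1.18, 7.1% | 1.45, 10.4% | 1.90, 15.5% |
| 10 (20) | 1.19, 7.2% | 1.38, 9.5% | 1.95, 16.0% | 2.90, 25.0% |

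**Unequal centres.** With a coefficient of variation (CV) of centre size, DE = 1 + [(1 + CV²)m − 1] × ICC. At an assumed CV of 0.8, 1 + CV² = 1.64. For 20 centres and ICC 0.02, DE = 1 + (16.4 − 1) × 0.02 = 1.31. For 10 centres and ICC 0.10, DE = 1 + (32.8 − 1) × 0.10 = 4.18.

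**More patients in the same centres.** Retrospective patients raise m. With 300 patients in 20 centres, m = 15; at ICC 0.05, DE = 1 + 14 × 0.05 = 1.70 and the error is 13.3%.

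**Simulation check** (200 patients, 2,000 runs per setting; each range runs from equal to unequal centres):
- t-test on a centre-level factor: 20 centres, 9 to 15% at ICC 0.05 and 17 to 21% at 0.10; 10 centres, 16 to 21% and 26 to 33%.
- Chi-square of responder status on a centre-level factor: less inflated, because splitting the change into two classes weakens the correlation. 20 centres, 9 to 12% at ICC 0.05; 10 centres, 13 to 17%.
- t-test on a patient-level factor unrelated to centre: 4 to 6% in every setting.

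**In mmHg.** Assuming an SD of the change of 15 mmHg, the naive 95% half-width is 1.96 × 15/√200 = 2.1. At ICC 0.05 it becomes 2.1 × 1.204 = 2.5 with 20 centres, or 2.1 × 1.396 = 2.9 with 10.

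**The case against.** Several points on the other side stand and limit the finding.

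- **Centre-level tests are not announced.** A reader might infer that comparisons by type of centre or operator speciality are planned. The Protocol asks only for a description of the former and collects the latter as a variable. The predictors it targets come from the initial clinical and biological work-up, and such factors are not inflated if unrelated to centre.
- **Size is not fixed.** A reader might infer error rates well above 5%. The Protocol gives no number of centres, no ICC and no alpha. At ICC 0.01 with 20 to 40 centres the error is only about 5 to 7%.
- **The ICC may be small.** TYPE OF DATA COLLECTED specifies how office and home blood pressure are measured, so measurement is partly standardised. The endpoint is a within-patient change, so a constant local bias cancels.
- **Effective sample size.** A reader might infer that it falls to the number of centres for a centre-level variable. That needs DE = m, that is ICC = 1. DE of 1.31 to 4.18 leaves 200/1.31 = 153 down to 200/4.18 = 48.
- **No confidence interval is promised**, and an exhaustive register might justify treating centres as fixed. This stands only in part. The paired t-test rests on the same standard error. Exhaustiveness is an aim, whereas the data come from participating centres and patients who do not object. Reimbursement decisions look beyond those patients.
- **Centre could enter the multivariate analysis or a separate analysis plan.** It could, so one cannot say that every planned analysis ignores centre. But the Protocol itself commits to the before/after and univariate tests, and an unspecified model elsewhere does not correct them.

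**Conclusion.** The point holds for the tests that the Protocol names. They ignore centre in a registry where care and follow-up are run locally. If the ICC is above zero, the standard error of the mean change is too small by a factor √DE for inference beyond these centres, and a centre-level variable in the responder comparison is tested above its nominal level.

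With 200 patients in equal centres, true error at a nominal 5% is about 6% (20 centres, ICC 0.01), 10% (20 centres, ICC 0.05) and 25% (10 centres, ICC 0.10). It is higher with unequal centres and somewhat lower for a chi-square on responder status. These figures rest wholly on the assumed ICC and number of centres. The documents do not support saying that every analysis is invalid or that the inflation is necessarily large. An extra 0.4 to 0.8 mmHg of half-width, as in the example, would not obviously change a descriptive before/after conclusion. The change is still worth making because it costs little and the results are intended for a policy decision.

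**What to change.** Amend the statistical analysis paragraph of the Protocol as follows.

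1. Primary endpoint and other before/after changes: keep the patient-weighted mean change, and report it with a 95% confidence interval from centre-clustered standard errors with small-sample degrees of freedom.
2. Wilcoxon, paired chi-square and Fisher alternatives: replace them with versions that allow for centre, since they share the independence assumption.
3. Responder and multivariate analyses: use the same clustering or a centre random effect.
4. Centre-level variables: test them only in that way; otherwise describe them without a p-value.
5. Report the number of centres, their sizes and the estimated ICC, so that readers can judge how much this mattered.

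No new data are needed, because the centre number is the first part of the patient code. The cost is a few lines of text, and intervals and p-values that are somewhat less favourable: by about √DE (1.04 to 1.38 with 20 equal centres and 1.09 to 1.70 with 10, for ICC 0.01 to 0.10), plus a little for the small-sample correction. A random-intercept mean would give patients from large centres less weight and could move the estimate itself, so the clustered version is preferable for the primary endpoint.
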